### 2.5.3 Handling of missing values/censoring/discontinuations

Missing data will not be replaced.

## 2.6 Safety analyses supporting secondary objectives

Safety evaluations on the safety analysis set will be based on the incidence, type, severity and consequences (e.g. study discontinuation) of an adverse event (AE) as well as on clinically significant changes in the patient's ECGs, vital signs, and clinical laboratory results. Summaries will be reported by cancer type [REDACTED] all patients together. Some summaries below may not be created for the short-term follow-up and long-term follow-up in either the interim or primary analysis if there is little safety data available.

### 2.6.1 Adverse events (AEs)

AE summaries will include all AEs occurring during on-treatment period. Specific listings will also be presented for the SAEs and AESIs occurring during short-term and long-term follow-up. All AEs collected in the AE eCRF page will be listed along with the information collected on those AEs e.g. AE relationship to study drug (separately for AEs related to any study drug, related to Lutathera and related to amino acid solution), AE outcome etc. The starting period of

the AEs (screening period, on-treatment, short-term and long-term follow-up periods) will be flagged in the listings.

AEs will be summarized by number and percentage of participants having at least one AE, having at least one AE in each primary SOC and for each PT. AEs will be coded using the MedDRA and assessed according to the CTCAE version 5.0. A participant with multiple occurrences of an AE will be counted only once in the respective AE category. A participant with multiple CTCAE grades for the same PT will be summarized under the maximum CTCAE grade recorded for the event. AE with missing CTCAE grade will be included in the 'All grades' column of the summary tables. In AE summaries, the primary SOC will be presented alphabetically, and the PTs will be sorted within primary SOC in descending frequency. The sort order for the PT will be based on their frequency in the total column.

The following AE summaries will be produced based on the FAS:

- Overview of adverse events and deaths (number and % of patients who died, with any AE, any SAE, any dose reductions/interruptions, any fatal SAEs, etc.);
- AEs regardless of study drug relationship by SOC, PT, and severity;
- AEs suspected to be study drug related by SOC, PT, and severity;
- AEs leading to discontinuation regardless of study drug relationship by SOC, PT, and severity;
- SAEs regardless of study drug relationship by SOC, PT, and severity;
- AEs leading to dose interruption/adjustment by SOC, PT, and severity;
- SAEs suspected to be study drug related by SOC, PT, and severity;

In addition, all AEs and SAEs with a start date in the short term and long-term follow-up will be listed separately.

#### **2.6.1.1 Adverse events of special interest / grouping of AEs**

During the treatment period, all AESIs are to be reported to the Sponsor irrespective of causality. During the follow-up period, AESIs are to be reported only if considered related to the study treatment except for all secondary malignancies which need to be reported as AESIs irrespective of causality. The AESIs represent main risks of Lutathera and amino acid treatment reported in adults, as well as potential risks in pediatric population.

The selection of the AESIs will be initially based on the classification of the AEs as reported in the Adverse Event eCRF page.

Additional groupings of AESIs above and beyond those flagged in the eCRF may also be examined in this study. These groupings are defined using MedDRA terms, SMQs (standardized MedDRA queries), HGLTs (high level group terms), HLT (high level terms) or PTs. Customized SMQs (Novartis MedDRA queries, NMQ) may also be used. A NMQ is a customized group of search terms which defines a medical concept for which there is no official SMQ available or the available SMQ does not completely fit the need. It may include a combination of single terms and/or an existing SMQ, narrow or broad.

The grouping of AEs in AESI according to project standards will be specified in the electronic Case Retrieval Strategy (eCRS) or separate listing in case of the AESI category is not included in the eCRS, and may be regularly updated.

All AESI categories will be summarized for those events occurring on-treatment. Events starting during the short-term and long-term follow-up periods will be listed.

## **2.6.2 Deaths**

Separate summaries for on-treatment and all deaths (including short-term and long-term follow-up deaths) will be produced by the cause of death.

All deaths will be listed, post treatment deaths will be flagged. A separate listing of deaths prior to starting treatment will be provided for all screened participants.

## **2.6.3 EudraCT and clinicaltrials.gov requirements for AEs and Death summaries**

For the legal requirements of clinicaltrials.gov and EudraCT, two on-treatment tables are required.

- On-treatment deaths resulting from SAEs suspected to be study drug related and SAEs regardless of study drug relationship by SOC and PT;
- Non-serious AEs regardless of study drug relationship, with an incidence rate greater than 5% in the respective cancer type by SOC and PT.

These summaries will include any events starting or worsening in the on-treatment period.

If for the same participant, several consecutive AEs (irrespectively of study treatment causality, seriousness, and severity) occurred with the same SOC and PT:

- a single occurrence will be counted if there is  $\leq 1$  day gap between the end date of the preceding AE and the start date of the consecutive AE;
- more than one occurrence will be counted if there is  $> 1$  day gap between the end date of the preceding AE and the start date of the consecutive AE.

The presence of at least one SAE / SAE suspected to be study drug related / non SAE has to be checked in a block e.g., among AEs in a  $\leq 1$  day gap block, if at least one SAE is occurring, then one occurrence is calculated for that SAE.

## 2.6.4 Laboratory data

The routine laboratory tests are assessed locally at each investigational site. The summaries will include all on-treatment assessments available for the lab parameter collected no later than 56 days after the last study treatment administration date (see Section 2.1.1) as well as including all short-term and long-term assessments cumulatively in separate summaries.

The following summaries will be produced for hematology, biochemistry and urinalysis laboratory data as well as for safety biomarkers (by laboratory parameter):

- Worst on-treatment CTC grade (regardless of the baseline status). Each participant will be counted only for the worst grade observed on-treatment.
- Shift tables using CTC grades to compare baseline to the worst on-treatment value.
- For laboratory tests where CTC grades are not defined, shift tables using the low/normal/high/(low and high) classification to compare baseline to the worst on-treatment value.

These summaries will be repeated including the short-term and long-term follow-up periods, respectively.

The following listings will be produced for the laboratory data:

- Listings of all laboratory data, with CTC grades and classification relative to the laboratory normal range. Lab data collected during the short-term and long-term follow-up periods will be flagged.
- Listing of all CTC grade 3 or 4 laboratory toxicities

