## 2 Objectives and endpoints

**Table 2-1 Objectives and related endpoints**

|                  | Objectives   | Endpoints   |
|------------------|---|--|
| Primary   | 

• Evaluate organ absorbed radiation doses from PRRT with Lutathera in adolescent patients with SSTR-positive GEP-NETs and PPGLs as a pooled cohort

• Evaluate safety and tolerability of Lutathera in adolescents with SSTR-positive GEP-NETs and PPGLs as a pooled cohort

  | 

• Target organ (e.g. kidney and bone marrow) absorbed radiation doses in adolescents with SSTR-positive GEP-NETs and PPGLs as a pooled cohort

• The incidence of adverse events (AEs) and laboratory toxicities after the 1st Lutathera administration in adolescents with SSTR-positive GEP-NETs and PPGLs as a pooled cohort

   |
| Secondary | 

• Evaluate cumulative safety of Lutathera in adolescents with SSTR-positive GEP-NETs and PPGLs as a pooled cohort

• Evaluate long-term safety of Lutathera in adolescents with SSTR-positive GEP-NETs and PPGLs as a pooled cohort

• Perform comparative assessment of dosimetry and pharmacokinetics (PK) between adolescent patients with GEP-NETs and PPGLs as a pooled cohort and adult patients using the extrapolation model developed for the clinical study

 | 

• The incidence of adverse events (AEs) and laboratory toxicities until 6 months after the last Lutathera dose (short-term follow-up) in adolescents with SSTR-positive GEP-NETs and PPGLs as a pooled cohort

• The incidence of adverse events (AEs) and laboratory abnormalities during the long-term follow-up of 5 years after the last Lutathera dose in adolescents with SSTR-positive GEP-NETs and PPGLs as a pooled cohort

• Calculated organ absorbed doses and PK parameters based on imaging/blood radioactivity concentration data from adolescent with SSTR-positive GEP-NETs and PPGLs as a pooled cohort patients compared to the predicted distribution / organ absorbed doses

 |

|  |  |  |
|--|--|--|
|  |  |  |
|--|--|--|

---

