### **12.5.2 Safety endpoints**

For all safety analyses, the FAS will be used. All listings and tables will be presented for all GEP-NET and PPGL participants as a pooled cohort.

Safety summaries (tables, figures) include only data from the on-treatment period with the exception of baseline data which will also be summarized where appropriate (e.g. change from baseline summaries) and long-term safety assessments which will be summarized separately. In addition, a separate summary for death including on treatment and post treatment deaths will

be provided. In particular, summary tables for adverse events (AEs) will summarize only on-treatment events, with a start date during the on-treatment period (treatment-emergent AEs).

The on-treatment period lasts from the date of first administration of study treatment to 56 days after the date of the last actual administration of Lutathera.

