**Document History – Changes compared to the previous final version of SAP**

Date	Time point	Reason for update	Outcome for update	Section and title impacted (Current)
10-Feb-2022	Prior to DB lock	Creation of the final version	N/A - First version	NA
25-May-2023	Prior to DB lock	Incorporate protocol amendment v 2.0.	Updated abbreviations  Minor grammatical updates  Add language for interim analysis  Language added for maximum PPGL population  Added statement about delivery of safety summaries dependent on available data  Added additional safety language to support AESIs pulled from eCRS	List of abbreviations  Throughout document  1 Introduction  1.1 Study Design  2.6 Safety Analyses  2.6.1.1 Adverse events of special interest/ grouping of AEs
26-mar-2024	Prior to primary DB lock	Incorporate protocol amendment v 3.0.	Added that the primary analyses will be by pooled cohort instead of separate cohorts.  Clarified that AESIs and SAEs during the short and long term follow-up will be listed only.	All sections  3 Sample Size  Section 2.6.1

Final

Date	Time point	Reason for update	Outcome for update	Section and title impacted (Current)
			Laboratory assessments and vital signs will be performed cumulatively instead of separately by periods	Section 2.6.4 and 2.6.5.2 [REDACTED] [REDACTED]

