### On-treatment assessment/event and observation periods

For adverse event reporting, the overall observation period will be divided into three mutually exclusive segments:

1. **Screening period:** from day of patient's informed consent to the day before first administration of study treatment
2. **on-treatment period:** from date of first administration of study treatment to 56 days (i.e. 8 weeks) after date of last actual administration of study treatment (including start and stop date).
3. **short-term follow-up period:** from day 57 after last administration of study treatment to day 183 (6 months) after date of last administration of study treatment
4. **long-term follow-up period:** starting from day 184 after last administration of study treatment

Safety summaries (tables, figures) include data from either on-treatment, short-term and long-term follow-up periods cumulatively with the exception of selection period data or baseline data which will also be summarized where appropriate. In particular, summary tables for adverse events (AEs) will summarize only on-treatment events, with a start date during the on-treatment period (**treatment-emergent** AEs) and specific listings of related SAEs and adverse events of special interest (AESI) will be provided for the short-term and long-term follow-up periods.

However, all safety data (including those from the short-term and long-term follow-up periods) will be listed and those collected during the short-term and long-term follow-up periods will be flagged.

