## 4 Change to protocol specified analyses

No change from protocol specified analysis was made.

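### The SAP's follow-up laboratory tables are cumulative with treatment, so none gives the incidence of abnormalities during long-term follow-up, which is a secondary endpoint

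*SAP*

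**What the plan says.** **Endpoint.** Protocol Table 2-1 sets two follow-up safety endpoints. One covers laboratory toxicities up to 6 months after the last dose. The other is the incidence of adverse events and "laboratory abnormalities during the long-term follow-up of 5 years after the last Lutathera dose". SAP Table 1 repeats both.

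**Protocol analysis.** Section 12.5.2 limits safety summaries to the on-treatment period, with stated exceptions. One exception is "long-term safety assessments which will be summarized separately".

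**SAP analysis.** Section 2.6.4 specifies worst-grade and shift tables on treatment: "Each participant will be counted only for the worst grade observed on-treatment". It brings in follow-up data "as well as including all short-term and long-term assessments cumulatively in separate summaries" and adds: "These summaries will be repeated including the short-term and long-term follow-up periods, respectively". Section 2.1.1 gives the general convention: "Safety summaries (tables, figures) include data from either on-treatment, short-term and long-term follow-up periods cumulatively". The same section starts the long-term period at day 184 after the last administration. The Document History describes the same intent: "Laboratory assessments and vital signs will be performed cumulatively instead of separately by periods".

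**Declared changes.** SAP 4 states: "No change from protocol specified analysis was made".

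**Listings.** SAP 2.6.4 also lists all laboratory data with CTC grades, flagging follow-up values, and separately lists all grade 3 or 4 laboratory toxicities.

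**The concern.** A worst-grade table that starts at the first dose can only stay level or get worse as follow-up is added. It answers how bad a parameter ever became. The endpoint asks what happened after day 183. The cumulative form suits the 6-month endpoint, which runs up to a time point, but not the long-term endpoint, which is confined to a period.

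The laboratory tables matter more in this trial than they might elsewhere. During follow-up only related SAEs and AESIs are recorded, plus all secondary malignancies (Protocol 8.4.1), and SAP 2.6.1 lists these without tabulating them. Laboratory tests and safety biomarkers are therefore the main systematic long-term safety data. Amendment 03 added endocrine and gonadal biomarkers to the long-term visits specifically to monitor for pituitary dysfunction. With cumulative tables alone, the report could neither tabulate a clean late period nor separate recovery from persistence.

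**Working it through.** The documents give no figure for these tables, so there is none to reproduce. The check has three steps.

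**1. Which reading of SAP 2.6.4 is meant?** The word *respectively* could suggest one table per period. However, the tables are repeated *including* the follow-up periods rather than restricted to them, and both SAP 2.1.1 and the Document History say cumulative. The text therefore gives on-treatment tables, then tables adding follow-up data, and none for day 184 onward alone.

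**2. What does each form show?** Take four hypothetical patients for one parameter:

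| Patient | Worst grade to day 183 | Worst grade from day 184 | Cumulative table | Table from day 184 |
|---|---|---|---|---|
| A | 3 | 0 | 3 | 0 |
| B | 3 | 3, after recovery | 3 | 3 |
| C | 1 | 3 | 3 | 3 |
| D | 3 | no value | 3 | not in denominator |

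A, B and D look the same in the cumulative table. Only C changes it. The same logic applies to the low/normal/high shifts used for tests without CTC grades: an early transient low conceals a later persistent low.

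**3. How large is the effect at grade 3/4?**

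Inputs:
- Adult grade 3/4 rates q in the NETTER-1 Lutathera arm (Protocol 4.3): anemia 0%, thrombocytopenia 1%, leukopenia 2%, neutropenia 3%, lymphopenia 44%. I treat these as on-treatment rates. Section 4.3 puts median onset in cycles 2 to 3 and median resolution within 6 months of the last cycle.
- N = 11 enrolled by 14-Dec-2023 (Protocol Amendment 03), all taken as treated; N = 8 is the planned minimum.
- Late grade 3/4 rate r: not in the documents. Assumed range 10% to 30%, independent of the earlier grade.

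Patients carried into the long-term table when every late value is normal = N × q:
- Lymphopenia: 11 × 0.44 = 4.84; 8 × 0.44 = 3.52.
- Other four parameters, N = 11: from 11 × 0 = 0 to 11 × 0.03 = 0.33.

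Cumulative count = N × [1 − (1 − q)(1 − r)]. Visible increase due to late events = N × (1 − q) × r. Expected count in a table from day 184 = N × r. The share of late grade 3/4 patients who add nothing is therefore q.

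| Lymphopenia, q = 44% | Table from day 184 | Cumulative count | Visible increase |
|---|---|---|---|
| N = 8, r = 10% | 0.80 | 3.97 | 0.45 |
| N = 8, r = 30% | 2.40 | 4.86 | 1.34 |
| N = 11, r = 10% | 1.10 | 5.46 | 0.62 |
| N = 11, r = 30% | 3.30 | 6.69 | 1.85 |

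For neutropenia (q = 3%, N = 11, r = 10%) the visible increase is 11 × 0.97 × 0.10 = 1.07, against 1.10 in a table from day 184. Across the four parameters other than lymphopenia, 0% to 3% of late grade 3/4 patients would be masked. Positive correlation between early and late grades would raise these shares.

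**The case against.** The best defence is that nothing is lost. Late values are listed, graded and flagged, and grade 3/4 values have their own listing. With 8 to 11 patients these can be read one by one. A late grade above every earlier grade does move the cumulative count, and comparing the on-treatment table with the repeated ones would show it. Protocol 12.5.2 also promises laboratory statistics by visit. All of this stands, and it limits the harm. It does not supply the endpoint: a listing has no pre-specified numerator or denominator, SAP 2.6.4 lists no by-visit laboratory table, and by-visit statistics are not an incidence.

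A second defence is that the SAP does put follow-up data in separate summaries, so Protocol 12.5.2 is met. That is arguable on the wording alone. It does not meet the endpoint in Table 2-1, which refers to events during the period.

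A reader might infer that late toxicity in general is hidden, or that a late myelodysplastic syndrome or leukaemia could go unseen. The documents do not support this. Secondary malignancies are reported as AESIs irrespective of causality until follow-up ends (Protocol 10.1.5), and SAP 2.6.1.1 lists AESIs starting in follow-up. Nor can the 44% be applied to other parameters. It belongs to lymphopenia, which Protocol 4.3 regards as no major infection concern and Table 6-4 exempts from dose modification.

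**Conclusion.** The concern holds in a limited form. As written, SAP 2.6.4 provides no table that estimates laboratory abnormalities during long-term follow-up. Its cumulative tables carry earlier abnormalities forward and do not register late ones of equal or lower grade. This departs from the endpoint and, on its natural reading, from Protocol 12.5.2, so the SAP 4 statement is not accurate.

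The distortion is large for lymphopenia: about 4.8 of 11 patients, or 3.5 of 8, shown at grade 3/4 with entirely normal late values. At grade 3/4 it is small for the other four hematology parameters. For lower grades and for renal and endocrine tests the documents give no rates, so the size is unknown. These figures assume that adult rates carry over to adolescents; the masked shares also assume that early and late grades are independent.

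This is a should-fix, not a must-fix. The endpoint is secondary and descriptive, no hypothesis is tested, and the primary endpoints and sample size are unaffected. The final analysis waits for 5 years of follow-up, so the table can still be pre-specified.

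**What to change.** - In SAP 2.6.4, add worst-grade and baseline-shift tables, including the safety biomarkers, restricted to values from day 184 after the last administration. Use patients with at least one value of that parameter in the period as the denominator, and state how many have none.
- Keep the cumulative table through day 183 for the endpoint that runs to 6 months.
- If the sponsor prefers cumulative tables only, declare and justify that in SAP 4.
- Optional: a shift from the last value before day 184, which would separate persistence from new onset, and matching tables for vital signs in SAP 2.6.5.2. Neither is required by the endpoint.

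The cost is SAP wording and one extra set of tables from data already collected. No visit, sample or patient is added.

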### **6.2.2 Prohibited medication**

Patients may not receive any other systemic therapy for the treatment of GEP-NET or PPGL (chemotherapeutic, biologic, or any investigational agent) other than Lutathera and somatostatin analogues during the study treatment period.

Localized therapy such as surgery or external beam irradiation may be performed on additional site(s), provided that it does not affect study endpoint assessment. For a major surgery, treatment with Lutathera must be temporarily discontinued and can be restarted after 12 weeks from the date of surgery.

Somatostatin and its analogues competitively bind to somatostatin receptors. Therefore, administration of long-acting somatostatin analogues should be avoided within 4 weeks prior to the administration of Lutathera. If necessary, patients may be treated with short acting somatostatin analogues during the 4 weeks until 24 hours preceding Lutathera administration.

There is some evidence that corticosteroids can induce down-regulation of SST2 receptors. Therefore, as a matter of caution, repeated administration of high doses of glucocorticosteroids should be avoided during Lutathera treatment. The use of glucocorticosteroids should also be avoided as preventive anti-emetic treatment. In the case where the treatments previously provided for nausea and vomiting are insufficient, a single dose of corticosteroids can be used, as long as it is not given before initiating or within one hour after the end of Lutathera infusion.

The absence of inhibition or significant induction of the human CYP450 enzymes, the absence of specific interaction with P-glycoprotein (efflux transporter) as well as OAT1, OAT3, OCT2, OATP1B1, OATP1B3, OCT1 and BCRP transporters in preclinical studies suggest that Lutathera has a low probability of causing significant other drug-drug interactions.

There is no restriction for concomitant medications during the follow-up period.

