### **Post treatment anti-cancer therapy**

Anti-neoplastic therapies since discontinuation of study treatment will be listed and summarized by ATC class, preferred term by means of frequency counts and percentages using FAS.

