### **5.3 Laboratory parameters derivations**

Grade categorization of lab values will be assigned programmatically as per NCI Common Terminology Criteria for Adverse Events (CTCAE) version 5.0. The calculation of CTCAE grades will be based on the observed laboratory values only, clinical assessments will not be taken into account. The latest available version of the document based on the underlying CTCAE version 5.0 at the time of analysis will be used. For laboratory tests where grades are not defined by CTCAE v5.0, results will be graded by the low/normal/high (or other project-specific ranges, if more suitable) classifications based on laboratory normal ranges.

A severity grade of 0 will be assigned for all non-missing lab values not graded as 1 or higher. Grade 5 will not be used. For laboratory tests that are graded for both low and high values, summaries will be done separately and labelled by direction, e.g., sodium will be summarized as hyponatremia and hypernatremia.

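### The cumulative follow-up laboratory tables may mix Lutathera toxicity with that of later anticancer therapy, because no planned laboratory output separates values at its start

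*SAP*

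**What the plan says.** SAP section 2.6.4 produces worst-grade and baseline-to-worst shift tables for hematology, biochemistry, urinalysis and safety biomarkers. The counting rule is one worst grade per person: "Each participant will be counted only for the worst grade observed on-treatment". The tables are then extended: "These summaries will be repeated including the short-term and long-term follow-up periods, respectively". The opening paragraph of the same section describes the extension as "as well as including all short-term and long-term assessments cumulatively in separate summaries".

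The on-treatment window runs "from date of first administration of study treatment to 56 days (i.e. 8 weeks) after date of last actual administration of study treatment". The long-term period is defined only by its start, "starting from day 184 after last administration of study treatment". Neither follow-up period ends at, or is divided by, new anticancer therapy. SAP section 5.3 fixes how grades are assigned: "The calculation of CTCAE grades will be based on the observed laboratory values only, clinical assessments will not be taken into account".

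Protocol section 6.2.2 bars other systemic antitumour therapy, apart from somatostatin analogues, during the treatment period, and then says: "There is no restriction for concomitant medications during the follow-up period". Protocol section 4.3 has the six-monthly long-term visits record further anticancer treatment and draw laboratory samples. SAP section 2.4.2 says of the therapy data: "Anti-neoplastic therapies since discontinuation of study treatment will be listed and summarized by ATC class", and also by preferred term.

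**The concern.** The repeated tables serve the secondary objective on long-term safety of Lutathera, whose endpoint includes laboratory abnormalities over five years after the last dose (Protocol Table 2-1, SAP Table 1). Participants have metastatic or inoperable disease, and those who stop study treatment early also continue into full follow-up (Protocol sections 6.5.2 and 9.1.1). Some may go on to other treatment. Protocol section 1.2 names chemotherapy, everolimus, radionuclide therapy and, for PPGL, iobenguane I 131 among the options.

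The protocol's main Lutathera risks are to marrow and kidney. A worst-value rule applied to every later assessment can pick up a cytopenia or a change in renal function that arises under a different agent, and a single-arm study has no comparator to separate the two. Follow-up adverse events are listed rather than tabulated (SAP sections 2.6.1 and 2.6.1.1). The laboratory tables therefore supply the main tabulated toxicity rates for follow-up, and they apply no attribution filter.

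**Working it through.** The plan gives no figure on this point. Its n = 8 detection probability does reproduce (1 − 0.7⁸ = 94.2%), but nothing in that calculation depends on how follow-up values are handled. The check is therefore of the text first, then of size.

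**1. Is there a split anywhere in the readable text?**
- Tables: cumulative over all short-term and long-term assessments, with no cut at new therapy (SAP 2.6.4).
- Grades: from the observed value alone (SAP 5.3).
- Laboratory listing: flagged by follow-up period, not by later therapy. Grade 3 and 4 values have their own listing, also without a therapy flag (SAP 2.6.4).
- Therapy data: a separate listing and frequency table, not linked to laboratory values. Concomitant therapies starting more than 56 days after the last dose are flagged in their own listing (SAP 2.4.2).
- Censoring: Protocol 12.4.3, on the primary endpoints, defers the rules to the SAP. SAP 2.5.3 names censoring in its heading but says only that missing data are not replaced.

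Nothing found separates laboratory values at new therapy. Redacted SAP text cannot be checked, though the visible redactions lie outside the laboratory section.

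**2. Can such values reach the tables?** Scheduled long-term visits are six months apart, so a short nadir may be missed. Unscheduled assessments do count towards worst-case values (SAP 2.1.1, Unscheduled visits). Capture is possible but not assured.

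**3. Effect of one participant.** Let n be the denominator: 8 is the planned minimum (Protocol 12.8), and 11 had been enrolled by 14-Dec-2023 (Amendment 03). The shift is 100/n, provided the participant had no earlier grade 3/4 value for that parameter.
- n = 8: 100/8 = 12.5 points. 0/8 (exact 95% CI 0 to 36.9%) becomes 1/8 = 12.5% (0.3 to 52.7%).
- n = 11: 100/11 = 9.1 points. 0/11 (0 to 28.5%) becomes 1/11 = 9.1% (0.2 to 41.3%).

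**4. How often?** The documents do not say. As an assumption only, let q be the share starting new therapy (20 to 60%) and r the chance that this puts a new grade 3/4 value into the table (10 to 50%), so qr runs from 0.02 to 0.30.
- Chance of at least one affected participant when nobody has an earlier grade 3/4 value, 1 − (1 − qr)ⁿ: for n = 8, 1 − 0.98⁸ = 0.15 to 1 − 0.70⁸ = 0.94; for n = 11, 1 − 0.98¹¹ = 0.20 to 1 − 0.70¹¹ = 0.98.
- Tabulated rate when the rate without new therapy is b = 10%, from b + (1 − b)qr: 0.10 + 0.90 × 0.02 = 11.8% to 0.10 + 0.90 × 0.30 = 37.0%.

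The width of these ranges shows that the frequency cannot be settled from the documents.

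**5. Time during which new therapy is permitted.** With four doses on schedule, the last is given 24 × 7 = 168 days after the first. The share of the covered time lying more than 56 days after the last dose is (5 × 365.25 − 56)/(168 + 5 × 365.25) = 1770.25/1994.25 = 89%. This is time in which new therapy is allowed, not time spent on it.

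**The case against.** A reader might infer that later toxicity will be counted as long-term Lutathera toxicity. The documents do not support that. It happens only if a participant starts new therapy and then records a grade worse than any earlier one. The tables assign no cause, and all analysis is descriptive. In a cumulative table an earlier high grade masks a later one. Grade 3/4 lymphopenia occurred in 44% of the Lutathera arm of NETTER-1 (Protocol 4.3), so for lymphocytes this masking could be common.

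Nor is it right to infer that the therapy data go unused or that attribution is absent. Post-treatment therapy is listed and summarized. Clinically significant laboratory values are adverse events, and for each event the investigator judges causality, weighing concomitant therapy among other causes (Protocol 10.1.1). In follow-up only related serious events and related events of special interest are recorded, plus all secondary malignancies (Protocol 8.4.1). The special-interest definitions cover marrow and kidney. With 8 to 11 patients, a reader could match grade 3/4 rows to therapy dates by hand.

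The cumulative form is also deliberate: the SAP document history records the move away from separate periods. Counting every value protects against missing late marrow harm. Cutting at new therapy could remove such signals, and the cut is probably informative because patients who progress would leave the table early.

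Most of this stands, and it is why the cumulative tables should remain the main presentation. It does not close the gap. The attributed events are listings only, no planned output links therapy dates to laboratory values, and the SAP does not say that values after new therapy are included by intent.

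**Conclusion.** The point holds as a limited one. The follow-up worst-grade and shift tables may include values obtained after new anticancer therapy, so the long-term rates can mix two sources under an endpoint named for Lutathera. Each affected participant with no earlier equal or worse grade adds 12.5 points to a grade 3/4 rate at n = 8, or 9.1 points at n = 11. Taking 11 as the denominator assumes that all enrolled patients were treated. How many participants would be affected is unknown, and the ranges for q and r above are assumptions.

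The on-treatment tables end 56 days after the last dose, and the primary safety tables cover the first cycle only. Both are essentially unaffected. This is an inexpensive gain in interpretability, not an error in the planned main tables.

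**What to change.** In SAP section 2.6.4:

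- Keep the cumulative follow-up tables as the main presentation, and state that they include values regardless of later anticancer therapy.
- Add, as a supportive analysis, the same follow-up worst-grade and shift tables restricted to values before the first new anticancer therapy. Define which therapies count and how an incomplete start date is handled; SAP 5.1.1 limits its date imputations to analyses of duration. Report how many participants are truncated and the follow-up time that remains.
- Flag values after that date in the laboratory listings, including the grade 3/4 listing.

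Further anticancer treatment is already recorded at the long-term visits, so no new assessment is needed and patient care does not change. The cost is one extra set of tables and one derived date. The restricted version has shorter and possibly informatively truncated follow-up and could lose late marrow events, so it should always be shown beside the cumulative one. The final analysis waits for five years of follow-up or withdrawal, so the rule can be fixed before those data are complete.
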